Remote Ischemic Conditioning (RIC) in Recipients of Brain Death Donor Livers –

A Feasibility and Safety Study

NCT02635347

October 1 2017

RIC Liver Recipients – Data Analysis Plan

RIC Liver Recipients – Data Analysis Plan

Available Data

- RECIPIENT Baseline Characteristics
 - Study Group
 - Hospital Days (#)
 - Post-Transplant Hospital Days (#)
 - Age, years
 - Gender
 - Ethnicity
 - American Indian/Alaska Native
 - Asian
 - Native Hawaiian
 - African American
 - Hispanic/Latino
 - White
 - More than 1 race
 - Unknown/not reported
 - Height
 - Weight
 - BMI
 - Beta blockers at transplant (y/n)
 - CCB at transplant (y/n)
 - Primary Etiology, Secondary etiology
 - EtOH
 - HBV
 - HCV
 - Cryptogenic/NAFLD
 - AIH
 - PBC
 - PSC
 - Budd-Chiari
 - Wilson's
 - Alpha-1 Antitrypsin
 - Biliary atresia
 - Other
 - HCC (y/n) – based on path report
 - HTN
 - CAD
 - Hx of MI
 - Peripheral vascular disease

- Peripheral neuropathy
- HIV
- Asthma
- COPD
- PNA
- Current smoker
- DM
- CKD
- On dialysis at time of Tx
- Serum creatinine
- eGFR
- Total Bilirubin
- INR
- MELD
- Pressors (y/n)
- Hypertonic saline (y/n)
- Mechanical ventilation (y/n)
- Days of mechanical ventilation
- Donor Baseline Characteristics
 - Age, years
 - Gender
 - Race
 - White
 - African American
 - Hispanic/Latino
 - Asian
 - Native American
 - Other
 - Height
 - Weight
 - BMI
 - Cause of death
 - Hospital days
 - OPO
 - Local
 - Regional
 - National
 - Donor receiving glucocorticoids
 - Donor on sulfonylureas
 - Pre-recovery biopsy performed
 - Macrosteatosis
 - Microsteatosis

- DRI
- Operative Variables
 - Anesthesia Maintenance agent (each y/n)
 - Sevo
 - Iso
 - Des
 - Other
 - Propofol used for induction (y/n)
 - Surgery length (min)
 - CIT (min)
 - WIT (min)
 - Veno-venous bypass used (y/n)
 - Piggypack or bicaval
 - Crystalloid (liters)
 - Albumin (liters)
 - RBC (units)
 - FFP (units)
 - Platelets (units)
 - Cryo (units)
 - Other fluid (likely nothing in this field)
 - UOP (liters)
 - EBL (liters)
 - Post-implantation biopsy (y/n)
 - Fields exist for %macro and %microsteatosis but these are all empty because the slides have not been reviewed.
- POST-Operative Variables
 - Propofol for sedation POST-OP (y/n)
 - ICU LOS (days)
 - POD 0-7 (8 values total)
 - AST
 - ALT
 - Total Bilirubin
 - INR
 - Creatinine (if not on HD to begin with and if not already in stage III AKI pretransplant)
 - Time to extubation
 - Reintubated within 7 days (y/n)
 - Early allograft dysfunction – EAD (y/n)
 - Prolonged respiratory insufficiency – PRI (y/n)
 - Stage 2 AKI (y/n)
 - Stage 3 AKI (y/n)
 - Pre- and post-transplant dialysis and whether or not it was discontinued in the hospital

- Time to dialysis discontinuation
- Clavien Dindo – all for 30 day complications
 - 3b (y/n)
 - 4a (y/n)
 - 4b (y/n)
 - 5, ie. Death (y/n)
 - Highest complication grade
 - Any complication greater than or equal to 3b (y/n)
 - Number of 3b or higher complications
- Survival PATIENT – 90 days
 - (y/n) and number of days
- Survival GRAFT – 90 days
 - (y/n) and number of days
- Dialysis – 90 days
- Creatinine at 90 days if not on dialysis
- eGFR at 90 days
- Completed study (y/n)

Statistical Analysis Plan

No comparison (one group)

- All feasibility data
 - Proportion of all patients who tolerated all 6 interventions
 - Proportion of patients who were intubated for all 6 interventions
 - Proportion of patients who were extubated for at least one intervention and tolerated all 6 interventions
 - For extubated patients: number of interventions tolerated while extubated. Break down into those who tolerated all 6 vs those who didn't tolerate all 6.
 - Mean/median pain score for patients receiving an intervention
 - Present as mean/median plus/minus STDEV/IQR for pain scores and number of interventions. Also histograms would be useful for these as the pain scores are likely going to end up being bimodally distributed.
 - Present as proportions with confidence intervals for all others.

Bivariate analyses – categorical data

Chi-squared or Fisher's exact tests.

- Recipient baseline characteristics
 - Gender, beta blockers at transplant (y/n), CCB at transplant (y/n), HCC (y/n) – based on path report, HTN, CAD, Hx of MI, Peripheral vascular disease, Peripheral neuropathy, HIV, Asthma, COPD, PNA, Current smoker, DM, CKD, On dialysis at time of Tx, Pressors (y/n), Hypertonic saline (y/n), Mechanical ventilation (y/n)
- Donor baseline characteristics
 - Gender, Donor receiving glucocorticoids, Donor on sulfonylureas, Pre-recovery biopsy performed (y/n)
- Operative Variables
 - Propofol used for induction (y/n), Veno-venous bypass used (y/n), Piggypack or bicaval, Post-implantation biopsy (y/n)
- POST-operative Variables
 - Propofol for sedation POST-OP (y/n), Reintubated within 7 days (y/n), **Early allograft dysfunction – EAD (y/n), Prolonged respiratory insufficiency – PRI (y/n)**, Pre- and post-transplant dialysis and whether or not it was discontinued in the hospital
 - Stage 2 AKI (y/n)
 - Stage 3 AKI (y/n)
 - These need to be discussed. The ideal method for comparison would be as an ordinal variable, using a CMH test. However, numbers may end up being low. Alternatively, can analyze as one y/n (ie. Stage 2 or 3 AKI) or using exact chi-squared.
- Clavien Dindo – all for 30 day complications

- 3b (y/n), 4a (y/n), 4b (y/n), 5 ie. Death (y/n)
 - These need to be discussed. We can analyze each individual complication grade using a 2x2 table. Analysis using an ordinal scale doesn't make sense, unless we take only the highest grade, for example.
 - Death also needs to be discussed. Later, we have 90 day mortality data (yes/no) as well as data regarding number of days survived. So we need to decide (a) if we are including death here at all, (b) if we end up analyzing 2x2 tables, is there any point to analyzing 30 day death separately from 90 days, I think no.
- Any complication greater than or equal to 3b (y/n)
- Other data
 - 90 day patient survival (y/n)
 - Can also analyze using Kaplan-Meier estimates
 - Should we consider gathering the data past 90 days? Our protocol does not say we would do this.
 - 90 day graft survival (y/n)
 - Can also analyze using Kaplan-Meier estimates
 - Patient on dialysis at 90 days (y/n)

Chi-squared or Exact Chi-squared tests (categorical variables with more than two levels for the outcome).

- Recipient baseline characteristics
 - Ethnicity, Primary/secondary etiology of cirrhosis,
- Donor baseline characteristics
 - Ethnicity, OPO (local/regional/national), Cause of Death,
- Operative variables
 - Anesthesia type
- POST-operative variables
 - Stage 2 / Stage 3 AKI (see discussion above)
- Clavien-Dindo
 - Complication grades (see discussion above)

Cochran–Mantel–Haenszel test for Ordinal Data

- Stage 2/3 AKI, Complication grades (see discussion above)

Bivariate analyses – Continuous Data

Student's T-Test vs Mann-Whitney U test

- Recipient baseline characteristics

- Hospital Days (#), Post-Transplant Hospital Days (#), Age years, Height, Weight, BMI, Serum creatinine, eGFR, Total Bilirubin, INR, MELD, Days of mechanical ventilation
- Donor baseline characteristics
 - Age years, Height, Weight, BMI, Hospital days, Macrosteatosis, Microsteatosis, DRI
- Operative variables
 - Surgery length (min), CIT (min), WIT (min), Crystalloid (liters), Albumin (liters), RBC (units), FFP (units), Platelets (units), Cryo (units), Other fluid (likely nothing in this field), UOP (liters), EBL (liters)
 - Macro/microsteatosis if data become available
- POST-op variables
 - ICU LOS (days)
 - POD 0-7 (8 values total)
 - AST, ALT, Total Bilirubin, INR, Creatinine (if not on HD to begin with and if not already in stage III AKI pretransplant)
 - Here, we need to decide how the data will be analyzed. There are three options: day-by-day comparisons, an omnibus test such as a factorial ANOVA (there will be a problem with missing data if we do this), and bivariate longitudinal linear regression (my personal preference, this accounts for correlation between observations within a subject on different days but at the same time uses all the data)
 - Time to extubation
 - Time to dialysis discontinuation
- Clavien-Dindo
 - Number of 3b or higher complications
- Creatinine at 90 days, eGFR at 90 days.

Multivariate regression analysis

- Logistic regression
 - EAD, PRI, Stage 2/3 AKI
- Longitudinal linear regression
 - AST, ALT, Total bilirubin, INR, Creatinine

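### Baseline ventilation status is not used in the analysis of time to extubation and is not named as a covariate for prolonged respiratory insufficiency

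*SAP*

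**What the plan says.** - **Baseline field.** Under Available Data, the SAP lists a yes/no ventilation field and a duration field with the recipient baseline characteristics. The yes/no field is compared between groups by chi-squared or Fisher's exact test (Bivariate analyses – categorical data): "Pressors (y/n), Hypertonic saline (y/n), Mechanical ventilation (y/n"). The duration is compared by t-test or Mann-Whitney (Bivariate analyses – Continuous Data): "eGFR, Total Bilirubin, INR, MELD, Days of mechanical ventilation". Neither field is named in any outcome analysis.
- **PRI.** In the categorical section, "Prolonged respiratory insufficiency – PRI (y/n") is one of two outcomes set in bold and is tested in a 2x2 table. The multivariate section lists it for logistic regression, "EAD, PRI, Stage 2/3 AKI", without naming covariates. The SAP does not define PRI.
- **Time to extubation.** "Time to extubation" appears among the post-operative continuous variables, for a t-test or Mann-Whitney test. It is in neither multivariate list: the logistic list is the one just quoted, and the longitudinal list covers the laboratory series given in the continuous section as "AST, ALT, Total Bilirubin, INR, Creatinine".
- **A related rule elsewhere.** One post-operative laboratory value is restricted by the patient's state before transplant: "Creatinine (if not on HD to begin with and if not already in stage III AKI pretransplant").

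**The concern.** A recipient who is already on a ventilator before transplant is likely to stay ventilated longer afterwards, whichever group they are in. The field is therefore expected to be strongly prognostic for both respiratory outcomes. It is already collected, yet the plan does not use it where it would help.

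Two things are at stake. First, if a few ventilated recipients fall mostly in one group, the unadjusted PRI difference and the comparison of extubation times carry that imbalance, and comparing the groups at baseline shows it without correcting it. Second, even with balanced groups, unexplained variation from this source reduces precision. The gap is widest for time to extubation, which has no adjusted analysis at all. For PRI a model exists, but nothing ensures that this field enters it.

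**Working it through.** **Inputs.** The SAP gives no sample size, alpha, allocation ratio, PRI rate or number of ventilated recipients, so there is no planned figure to reproduce. Everything below is an illustration with assumed values: 1:1 random allocation, two-sided 5% tests, 20 to 50 per arm, PRI of 80% if ventilated before transplant and 15% if not, and no treatment effect unless stated.

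**1. Shift from a chance imbalance in PRI.** Expected PRI in an arm of n with k ventilated recipients is (k × 0.80 + (n − k) × 0.15)/n. At n = 30:
- k = 1: (0.80 + 29 × 0.15)/30 = 17.2%
- k = 4: (3.20 + 26 × 0.15)/30 = 23.7%
- Difference: 3 × (0.80 − 0.15)/30 = 6.5 points

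The same gap of three recipients gives 3 × 0.65/20 = 9.8 points at 20 per arm and 3 × 0.65/50 = 3.9 points at 50. With PRI varied over 10–20% (not ventilated) and 70–100% (ventilated), a 3 v 0 split gives 7.5 to 13.5 points at 20 per arm and 3.75 to 6.75 at 40.

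**2. Would that shift be significant?** Exact binomial calculation for the 1 v 4 split at 30 per arm gives a rejection probability of 3.3% for Fisher's test and 6.8% for the uncorrected chi-squared test. Averaged over random allocation (2, 4 or 6 ventilated recipients in total, 20 or 40 per arm, PRI 100% v 20%), Fisher's type I error is 2.3% to 2.9%.

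**3. How likely is a gap of three or more?** The number ventilated in each arm is taken as Binomial(30, v).

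| Assumed proportion ventilated, v | P(gap ≥ 3), 30 per arm |
|---|---|
| 10% | about 27% |
| 5% | 13% |
| 2% | 2.6% |
| 1% | 0.5% |

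At v = 10% the figure is 18% at 20 per arm and 40% at 50.

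**4. Variation explained in PRI.** With v = 0.10, overall PRI is p = 0.10 × 0.80 + 0.90 × 0.15 = 0.215. The share of variance is v(1 − v)(0.80 − 0.15)²/[p(1 − p)] = 0.0380/0.1688 = 0.225.

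**5. Time to extubation.** Simulation at 30 per arm, with outcomes shifted by 2 SD in ventilated recipients: moving from Mann-Whitney to van Elteren raises power from 0.49 to 0.58 with 10% ventilated, and from 0.58 to 0.59 with 2%. Type I error is near 5% for both tests. A repeat with normal outcomes and a 0.6 SD treatment effect agreed to about 0.01.

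**6. Which stratified test for PRI?** At 30 per arm, 10% ventilated, 80%/15% and an odds ratio of 0.35, simulated power is 0.19 for the planned chi-squared test, 0.11 for Fisher, 0.22 for the asymptotic Cochran-Mantel-Haenszel (CMH) test and 0.15 for the exact CMH test. The exact version loses power against chi-squared.

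**The case against.** The plan can be defended on several points, and most of the defence stands.

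- **Type I error.** A reader might infer that an imbalance of a few ventilated recipients would pass for a treatment effect. The calculations do not support that: under random allocation the planned tests keep their error rate, and a 6.5-point shift at 30 per arm would seldom be significant. What remains is a shifted estimate and lost precision.
- **PRI already has an adjusted analysis.** This is correct, and the baseline comparison would display an imbalance. The remaining gap is that covariates are unnamed, which is true of every model in the SAP.
- **Prevalence.** If 1–2% of recipients were ventilated, an imbalance of three would be rare and the power gain negligible. If eligibility rules in the protocol, which is not shown, exclude such recipients, the issue disappears.
- **The creatinine rule.** A reader might see a contradiction between that restriction and its absence here. The analogy is loose: the creatinine rule concerns a value altered by dialysis or already at the worst stage, which is not the same as adjusting for a prognostic factor.
- **Timing.** "Days of mechanical ventilation" is not stated to be before transplant. The same recipient baseline list includes hospital days after transplant, so its place in the list does not settle the matter.

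None of this supplies an adjusted analysis for time to extubation or names the field for PRI.

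**Conclusion.** The point holds as a modest, inexpensive improvement, not as a flaw that invalidates a planned test. A yes/no ventilation field listed at baseline is left out of the time-to-extubation analysis and is not named for the PRI model. Under the illustrative assumptions, a gap of three ventilated recipients moves expected PRI by 6.5 points at 30 per arm, and stratifying time to extubation adds about 0.09 to power if 10% are ventilated but only 0.01 if 2% are. The prevalence, PRI rates, arm sizes and 2 SD shift are all assumed. The size in this trial depends on how many recipients were ventilated, which the SAP does not give.

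**What to change.** 1. Confirm that the yes/no field records status before transplant. Do not rely on the duration field until its timing is also confirmed.
2. Keep all patients in both analyses.
3. Compare time to extubation with a van Elteren test (stratified Mann-Whitney) using pre-transplant ventilation as the stratum.
4. Name that field as a pre-specified covariate in the PRI logistic model, and report the result beside the planned unadjusted 2x2 test. An exact CMH test should not be required, since it can have less power than the planned chi-squared test.

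The cost is SAP wording only, because the field is already collected. The ventilated stratum may be very small. If it is empty, the van Elteren test becomes the Mann-Whitney test, the covariate drops out, and the analysis is the planned one.

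### The SAP specifies no between-group effect estimate with a confidence interval, and several safety outcomes have only a hypothesis test

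*SAP*

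**What the plan says.** The title page calls the trial "A Feasibility and Safety Study". Under the heading No comparison (one group), the SAP gives a reporting rule for the feasibility data: means or medians with spread for pain scores and number of interventions, and "Present as proportions with confidence intervals for all others". Confidence intervals are mentioned nowhere else.

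For comparisons between groups, the SAP names these methods:

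- **Two-level outcomes** (reintubation, EAD, PRI, dialysis, any Clavien-Dindo complication of grade 3b or higher, 90-day patient and graft survival): "Chi-squared or Fisher's exact tests".
- **Clavien-Dindo grades**: undecided. One option reads "We can analyze each individual complication grade using a 2x2 table"; the highest grade as an ordinal variable is another.
- **AKI**: also undecided, between an ordinal CMH test, a single yes/no and an exact chi-squared test. On the ordinal option the SAP remarks "However, numbers may end up being low".
- **90-day patient and graft survival**: besides the yes/no test, "Can also analyze using Kaplan-Meier estimates".
- **Continuous outcomes**: "Student's T-Test vs Mann-Whitney U test". For the daily laboratory values three approaches are listed, and the author prefers longitudinal regression.
- **Multivariate regression analysis**: logistic models for EAD, PRI and AKI, and longitudinal models for five laboratory measures.

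The SAP names no risk difference, ratio, or mean or median difference. It also states no significance level, multiplicity rule or exploratory label.

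**The concern.** Safety is half of the question in the title. The SAP says how precision will be shown for the feasibility half and leaves it out for the safety half. A chi-squared or Fisher test asks whether the data are incompatible with no difference. It does not say how large an excess of complications, reintubation or dialysis remains plausible, and a reader of a safety study needs to know that. When events are few, a p-value above 0.05 is the likely result even if harm is materially increased.

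The converse risk comes from the number of tests. With many outcomes tested and none marked exploratory, a few nominally significant differences are to be expected by chance, and nothing in the SAP tells the reader how to weigh them.

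**Working it through.** The SAP states no sample size, event rate, significance level or number of tests, so it has no figure to reproduce. The arm sizes, event rates and 5% level below are assumptions.

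**1. Which outcomes have an estimate within reach?**

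- *A model or estimator is listed, but reporting of estimates or intervals is not stated:* 90-day patient and graft survival (optional Kaplan-Meier), EAD, PRI and AKI (logistic regression), AST, ALT, bilirubin, INR and creatinine (longitudinal regression).
- *Only a test is listed:* Clavien-Dindo grades, any complication of grade 3b or higher, number of such complications, reintubation, dialysis status and time to its discontinuation, ICU stay, time to extubation, 90-day creatinine and eGFR.

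**2. What would an interval show?** Assume an observed 20% event rate in both arms. The Newcombe 95% interval combines the Wilson limits (L, U) of each arm. With equal arms its half-width is √[(0.20 − L)² + (U − 0.20)²].

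- n = 20 per arm: L = 0.081, U = 0.416; √(0.119² + 0.216²) = 0.247.
- n = 50 per arm: L = 0.112, U = 0.330; √(0.088² + 0.130²) = 0.157.

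Power of the two-sided Fisher test at 5%, by exact enumeration, for a true 20% against 40%:

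| Per arm (assumed) | 95% CI half-width, 20% vs 20% | Fisher power, 20% vs 40% |
|---|---|---|
| 20 | ±24.7 points | 19% |
| 30 | ±20.2 points | 30% |
| 40 | ±17.6 points | 41% |
| 50 | ±15.7 points | 52% |

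So with identical observed rates the data would still allow an excess of about 16 to 25 points. A true doubling would be missed in 48% (100 − 52) to 81% (100 − 19) of such trials.

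**3. How many outcome tests?** The count depends on the open choices.

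- *Leanest:* 4 (reintubation, EAD, PRI, dialysis discontinued) + 1 (AKI) + 1 (highest Clavien grade) + 1 (any ≥3b) + 3 (90-day patient survival, graft survival, dialysis) + 6 (ICU stay, time to extubation, time to dialysis discontinuation, number of ≥3b complications, 90-day creatinine, 90-day eGFR) + 5 (one model per laboratory measure) = 21.
- *AKI stages and Clavien grades tested separately:* AKI becomes 2 and grades become 4, so 21 + 1 + 3 = 25.
- *Adding the 8 multivariable regressions:* 25 + 8 = 33.
- *Adding everything else listed* (2 hospital-stay measures, 2 Kaplan-Meier, 2 CMH, post-operative propofol, days of ventilation): 33 + 8 = 41.
- *Laboratory values compared day by day:* 5 × 8 = 40 tests replace 5, adding 35. The range becomes 21 + 35 = 56 to 41 + 35 = 76.

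Expected false positives if no true differences exist = 0.05 × number of tests: 1.05 for 21, 1.65 for 33, 2.05 for 41, 3.8 for 76. The chance of at least one, if the tests were independent, is 1 − 0.95^k: 66% for 21, 82% for 33, 88% for 41, 98% for 76. Correlation between outcomes alters these probabilities but not the expected counts. Fisher's test with sparse data rejects less often than its nominal level, so the expected counts are nominal figures.

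**The case against.** The strongest reply is that this is a reporting omission. Naming a test does not forbid reporting proportions, and every 2x2 table holds the counts from which a risk difference and interval follow. That is true, and it is why the remedy is cheap. It does not remove the point: the SAP does specify intervals for one section, and followed as written it produces none for the safety comparisons.

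Some stronger readings are tempting, and the document does not support them:

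- *That the SAP offers significance tests and nothing else.* Kaplan-Meier estimates, logistic regression and longitudinal regression are all listed. The gap is that no estimate or interval is specified for reporting, and that a subset of outcomes has a test only.
- *That 40 to 75 tests are planned.* Such a count adds up options that the SAP marks as still to be discussed or as alternatives. It includes Kaplan-Meier curves for which no between-group test is named. Its upper end needs day-by-day laboratory comparisons, which the author does not prefer.
- *That non-significance will be taken as proof of safety.* The SAP never says so; this is a risk of the format.
- *That the SAP concedes low numbers throughout.* The remark about numbers concerns the ordinal AKI analysis alone, and a small sample is an inference.
- *That the bold type on EAD and PRI sets a testing hierarchy.* The SAP does not explain the bold.

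Two further parts of the objection stand. The independence figures are only indicative, since single Clavien grades are nested in the composite and 30-day death overlaps 90-day survival. Sample size, significance level and a primary comparison may well be in the protocol, which is not at hand.

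**Conclusion.** The point holds in this form: no between-group effect estimate with a confidence interval is specified for any outcome, and Clavien-Dindo complications, reintubation and dialysis have only a test. This can be read directly from the SAP and needs no assumption about sample size.

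The size of the consequence does rest on assumptions. At 20 to 50 per arm and 20% event rates, the interval is about ±25 to ±16 points and power to detect a doubling is 19% to 52%. These figures show what a bare p-value would hide; they do not measure this trial. The multiplicity part is secondary: about 21 to 76 outcome tests, hence about one expected false positive on the leanest count at a nominal 5%, with no exploratory label. The change should be made, but it concerns reporting and interpretation and leaves design and data collection untouched.

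**What to change.** - For each binary safety outcome, report the proportion in each group and the risk difference with a 95% confidence interval (Newcombe or exact).
- For continuous, survival and regression analyses, report the group-effect estimate with its 95% confidence interval.
- State that the safety conclusion rests on these intervals, in particular on how much excess harm they leave open, and not on p > 0.05.
- Label between-group p-values as exploratory unless the protocol names a primary comparison; if it does, name that comparison in the SAP.

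The cost is a few sentences in the SAP and one extra column in the tables. The small downside is that fewer results can be called significant. No additional data are needed.

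### Separate tests per Clavien-Dindo grade can show fewer 3b complications in the arm with worse events; cumulative cuts at 4a and 4b are not listed

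*SAP*

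**What the plan says.** In the SAP, *Bivariate analyses – categorical data*, the 30-day complications stand under chi-squared or Fisher's exact tests as four separate variables: "3b (y/n), 4a (y/n), 4b (y/n), 5 ie. Death (y/n"). The note beneath them says that the analysis is still open and offers one route: "We can analyze each individual complication grade using a 2x2 table". It then qualifies the other route: "Analysis using an ordinal scale doesn't make sense, unless we take only the highest grade, for example".

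Three further complication variables appear:

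- "Any complication greater than or equal to 3b (y/n"), in the same list of comparisons.
- "Highest complication grade", under *Available Data*. Complication grades are also named under the Cochran–Mantel–Haenszel (CMH) heading, with a reference back to the note above.
- "Number of 3b or higher complications", under *Bivariate analyses – Continuous Data*.

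The plan does not say whether a yes at a given grade means an event of exactly that grade or of that grade or worse. No variable is listed for 4a or worse, or for 4b or worse.

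For AKI, Stage 2 and Stage 3 are separate yes/no fields, but a preference is stated: "The ideal method for comparison would be as an ordinal variable, using a CMH test". The fallback reads: "Alternatively, can analyze as one y/n (ie. Stage 2 or 3 AKI) or using exact chi-squared".

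**The concern.** A yes/no safety variable should rise when patients do worse. A grade-specific 3b field need not. Its no group pools patients without any serious complication with patients whose only serious complication was 4a, 4b or death. If one arm moves patients from 3b into higher grades, its 3b count falls, and that table taken alone reads as benefit. The 4a table has the same property with respect to 4b and death.

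The variables that escape this false signal do not reveal the shift either. The 3b-or-higher variable is unchanged by movement within the severe range, and the number of such complications gives a 3b and a 4b equal weight. The SAP also asks whether 30-day death should be in this set at all. If it is dropped, a patient whose only event is death becomes a no in every remaining per-grade table.

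The study's title presents it as one of feasibility and safety, so a safety table that can point the wrong way deserves attention.

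**Working it through.** The SAP gives no sample size, event rates or error rate, so there is no stated figure to reproduce. All rates and the arm size below are assumptions chosen to show the mechanism.

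**1. What the fields mean.** If 3b (y/n) already meant 3b or worse, the separate 3b-or-higher field would duplicate it. The natural reading is therefore grade-specific. The highest-grade field, the count of complications and the remark on ordinal analysis suggest in turn that one patient may be a yes at several grades. So two codings are examined: one worst grade per patient, and any event of that grade.

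**2. One worst grade per patient.** Assumed distributions (none, 3b, 4a, 4b, death) are 60, 20, 10, 5, 5% in arm A and 60, 10, 10, 10, 10% in arm B, the worse arm.

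| Variable | Arm A | Arm B |
|---|---|---|
| 3b alone | 20% | 10% |
| 4a alone | 10% | 10% |
| 4b alone | 5% | 10% |
| Death | 5% | 10% |
| 3b or worse | 20+10+5+5 = 40% | 10+10+10+10 = 40% |
| 4a or worse | 10+5+5 = 20% | 10+10+10 = 30% |
| 4b or worse | 5+5 = 10% | 10+10 = 20% |

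The 3b row favours the worse arm, the 3b-or-worse row shows nothing, and the two cuts that the plan does not list show the direction.

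**3. How often this would be seen.** With 30 per arm, the chance that B has fewer 3b patients than A is the sum, over all counts i > j, of Bin(i; 30, pA) × Bin(j; 30, pB). At 20% v 10% it is 0.821. The chance that B has more patients at 4b or worse (10% v 20%) is the same, 0.821. Fisher's exact test on 3b reaches p < 0.05 in favour of B in about 0.095 of trials.

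**4. Any event of that grade.** Let f be the share of patients with a worse grade who also have a 3b. Then pA = 0.20 + 0.20f and pB = 0.10 + 0.30f.

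| f | pA | pB | Chance that B shows fewer 3b |
|---|---|---|---|
| 0 | 0.200 | 0.100 | 0.821 |
| 0.25 | 0.250 | 0.175 | 0.711 |
| 0.50 | 0.300 | 0.250 | 0.615 |
| 0.75 | 0.350 | 0.325 | 0.528 |
| 1 | 0.400 | 0.400 | 0.448 |

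At f = 1 the two rates are equal, so 0.448 is pure chance (ties make up the rest) and the distortion is gone.

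**5. A larger assumed shift.** Take 3b, 4a, 4b, death at 20, 10, 5, 5% v 5, 20, 10, 5%, one worst grade per patient, with counts set to their expected values. The 3b table is 4 v 1 (Fisher p = 0.34) at 20 per arm, 8 v 2 (p = 0.087) at 40 and 20 v 5 (p = 0.002) at 100. At 100 per arm, 3b or worse is 40 v 40, while 4a or worse is 20 v 35 (p = 0.026).

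**6. AKI.** Only if Stage 2 is coded as the worst stage reached does the same thing happen. At assumed stage 2/3 rates of 30/15% v 15/30% and 30 per arm, the worse arm shows fewer Stage 2 patients in 90% of trials. The Stage 3 table shows the harm equally often. The plan does not define this coding.

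**The case against.** The strongest reply is that the plan does not commit to per-grade tests. They are an option awaiting discussion, and the same note allows an ordinal analysis of the highest grade, which is collected and would detect the shift. That stands: the point is about an option that should be closed off, and a reader should not infer that the grades are analysed only as stand-alone yes/no variables.

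A reader might also infer that a shift to worse events must produce fewer 3b events. It need not. A patient with both a 3b and a 4a is a yes at both, and step 4 shows the effect fading as such patients become common. Nor does a lower count amount to a false finding: about one trial in ten reaches p < 0.05 in the misleading direction, even under the least favourable coding in that example. A reader who looks at the 4b and death rows would see the harm there.

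Two further stronger readings lack support. Nothing ranks the per-grade tables as the main between-group safety analysis. And nothing says that a Stage 3 patient is a no at Stage 2: that coding is undefined, the plan prefers an ordinal test, and it offers the combined Stage 2 or 3 variable. Stage 3 and grade 5 are the top of their scales, so those fields are already cumulative.

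What the reply does not remove is that the analysis sensitive to severity is mentioned but not adopted, and that the middle cuts are absent.

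**Conclusion.** The point holds in a conditional form. If the Clavien-Dindo fields are grade-specific, as the separate 3b-or-higher variable suggests, a 3b table tested on its own can favour the arm with worse events. The listed 3b-or-higher variable would not correct the impression, and no cut at 4a or worse or at 4b or worse is listed.

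On the assumed rates with 30 per arm, the chance that the worse arm shows fewer 3b runs from 82% (one worst grade per patient) to the chance level of about 45% (every patient with a worse grade also has a 3b). These figures show the mechanism and do not predict this trial. The AKI part is minor, because the plan's stated preference and its combined variable largely cover it. What remains there is that Stage 2 should not be tested alone.

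**What to change.** - Replace the four per-grade tests by cumulative cuts: 3b or worse, 4a or worse, 4b or worse, and death. Each is a yes if any field at or above the cut is a yes, so the derivation works under either coding.
- Name the highest-grade ordinal comparison (CMH), already mentioned in the plan, as the analysis to be read with these cuts.
- Report single-grade counts by arm as description, without a test, and state what a yes in each field means.
- For AKI, keep the ordinal CMH test, or the Stage 2 or 3 variable together with Stage 3. Do not test Stage 2 alone.

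The cost is a recoding of fields already held and a line or two in the SAP, with no new data. The drawback is that the cuts overlap: a death counts in all four. They must be read together as one picture of severity and not as independent tests.
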